Study progress and safety will be reviewed by the MPIs monthly (and more frequently if needed). Semi-annually, a progress report will be generated for the DSMB's review. The full DSMB will be convened twice per year to review the semi-annual report and discuss data and participant safety.

9.c. Content of DSM Report

The DSM report will include a brief description of the aim of the trial, baseline and demographic information, recruitment and retention, regulatory issues or data quality issues that have arisen, and AE/SAEs. The DSM report will be sent to the NIDA Program Officer annually.

The study team will specifically generate the following for the DSM report:

Interim CONSORT document (number screened, number consented, reasons not eligible, status of all participants enrolled in the study, number completed the study vs. withdrawn)

Actual vs. expected enrollment numbers

Gender, age, race, and ethnicity of enrolled participants

List and description of deaths, unanticipated problems, and SAEs

Summary table of AEs

List of protocol deviations, if any

Ongoing quality assurance and quality control procedures and findings.

The DSMB will determine whether 1) AE rates are with pre-study assumptions, 2) whether continuation of the study is justified, and 3) conditions under which the study would be prematurely terminated.

10. DSM Board Plan

10.a Members and Affiliation

[name]. – Director of Neuropsychiatric Modulation at the Providence Veterans Affairs Medical Center; Associate Professor of Psychiatry and Human Behavior at the Alpert Medical School of Brown University.

[name]. – Deputy Director of Intervention Studies at the New York State Psychiatric Institute; Professor of Psychiatry at Columbia University Medical Center.

10.b Frequency of Meetings

See 9.b

10. c Conflict of Interest

Pending

10.d. Protection of Confidentiality

Only de-identified data will be presented in DSMB reports.

10.e Monitoring Activities

See 9.a

10.f Communication plan to IRB, NIDA, and FDA

DSMB reports will be submitted to both the Butler Hospital IRB and NIDA.

References

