Grant Number: UH3DA047793

Title: tDCS to Decrease Opioid Relapse

MPIs: [name] and [name]

Medical Monitor: [name]

2. Summary of the Protocol:

2.a, 2.b Brief Description of the Protocol, Primary and Secondary Outcome Measures

This study has two phases. In phase one (UG3), we propose to use functional magnetic resonance imaging (fMRI) and electroencephalographic (EEG) to quantify changes in brain function and reported craving before and after administration of five sessions of transcranial direct current stimulation (tDCS) targeting the right dorsolateral prefrontal cortex (DLPFC). Opioid dependent participants (n=60) who recently initiated buprenorphine or methadone will be randomized to tDCS+Cognitive Control Network (CCN) priming stimulation vs. sham tDCS+CCN priming. Participants in their first month of prescribed buprenorphine or methadone will be assessed using fMRI and EEG, once prior to tDCS and again one week later after completion of 5 sessions of tDCS+CCN priming. With a focus on the craving outcome, we will use two task-based fMRI paradigms that challenge networks associated with craving (CR) and cognitive control (CCN), and will examine these and the salience network using resting state functional connectivity. We examine an additional validation measure of the effect of tDCS on the DLPFC – an oscillatory target -- EEG frontal theta power during working memory(WM). In this UG3 phase, fMRI and EEG will be expected to provide 1) validation of expected network and oscillatory changes from tDCS-targeting and 2) an effect size for DLPFC vs sham stimulation. Go/no go criteria for the UG3 phase will be demonstration of greater fMRI change in any node of the CR or CCN networks or enhanced frontal theta power during a WM task AND greater change (at least 10% difference between conditions, controlling for baseline craving) in subjective craving measured during a cue reactivity task or outside the fMRI following the tDCS+CCN priming intervention compared to sham tDCS+CCN priming.

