1) CR: Two 2x2 mixed ANOVAs will be used to determine whether mean response to cues during CR decline across nodes of the craving network (VS, amygdala, VMPFC), including salience network (AI, ACC) and increases in the CCN (MFG, IPL). Significant pre-post main effects and group x treatment interactions are predicted in each. Those who received tDCS+CCN priming are expected to exhibit greater change. Follow up analyses of individual nodes within each network and whole-brain voxel-wise contrasts will be conducted to inform phase 2 analyses.

2) n-Back: Two 2x2 mixed ANOVAs will be used to determine whether mean response to the n-Back challenge increases across nodes of the CCN (MFG, IPL) and the salience network (ACC and AI). Significant pre-post main effects and group x treatment interactions are predicted in each. Those who received tDCS are expected to exhibit greater change. Follow up analyses of individual nodes within each network and whole-brain voxel-wise contrasts will be conducted to inform phase 2 analyses.

3) Resting state: Two 2x2 mixed ANOVAs will be used to determine whether mean network coherence (functional connectivity) decreases across nodes of the craving network (VS, amygdala, VMPFC), including the salience network (AI, ACC) and increases in the CCN (MFG, IPL). Significant pre-post main effects and group x treatment interactions are predicted

in each. Those who received tDCS are expected to exhibit greater change. Parallel exploratory analyses will be conducted to examine resting state functional connectivity of the salience network and DMN.

In the UH3, neuroimaging analyses will generally parallel those described for UG3. We will use a 2x3 ANOVA (three time points) to test the hypothesis that tDCS+CCN priming will be superior to sham tDCS+CCN priming on both subjective and fMRI measures of craving and cognitive control at the end of 5 sessions and at 3-months post tDCS. This same analytical method will be used to test the effect of intervention on days of drug use at the end of 5 sessions and at 3-months. We will use the Pearson χ^2 -test of independence to compare tDCS+CCN priming to sham tDCS+CCN priming on relapse at 3-months.

FMRI data analyses

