EEG outcome measures analyses. We will conduct a repeated-measures ANCOVA with a within-subject factor of time (baseline and end-of-stimulation (EOS)), between-subject factor of intervention condition (active tDCS and sham) and covariates to test if there is a statistically significant difference in in the EEG outcome (Δtheta) across treatment groups. Pearson correlations will be used to examine beta PSD values in relation to craving scores. A separate ANCOVA with the same factors will be used to explore treatment group differences in resting state EEG beta PSD values. Covariates for both analyses will include the baseline measure of the evaluated outcome, as well as baseline variables found to vary significantly ($p < 0.05$) by intervention arm, or which significantly ($p < 0.05$) predict attrition at EOS. Post-hoc t-tests will be used to probe anticipated significant interactions.

5. Quality Assurance

All research personnel, will have formal training in research with human subjects (e.g., CITI training, NIH Human Subjects training). Drs. [name], [name], and [name] will provide training to and supervise research assistants. Research assistants will also have training in Good Clinical Practice.

Drs. [name] and [name] will be responsible for quality control of this study. They will review recruitment and retention reports, and AE reports on a weekly basis. The MPIs (or their designee) will inspect BL documents (consent forms, release of information) for completeness within a week after they are signed. The MPIs (or their designee) will also conduct protocol and data quality monitoring twice a year using a checklist. This monitoring will include reviewing other study records to ensure completeness.

6. Regulatory Issues

6.a, 6.c Reporting of SAEs, Non-Medication Trials

Drs. [name] and [name] will be responsible for overseeing the daily safety of all participants. There are several ways in which they will become aware of adverse events. First, research staff will ask participants about serious adverse events (as defined by Office of Human Research Protections (OHRP); e.g., inpatient hospitalization) at each research contact point (UG3: baseline, week 2 assessment, 5 tDCS appointments, 2 fMRI; UH3: baseline,

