Minimization. To minimize the risk of distress arising from the assessment procedure, only study staff that has been adequately trained in the assessment battery will complete all assessments, and senior study staff will supervise all assessment procedures. Individuals will also be advised that they may choose not to answer any question which they find upsetting. Further, during EEG and tDCS+CCN sessions, participants will be reminded they can stop the procedure at any time, if they get tired. All study procedures will be explained to the participants with an emphasis on the voluntary nature of the study. Furthermore, staff members will be trained to respect participants' wishes regarding their participation in the study or certain aspects of the study's procedure. There is minimal, if any, additional risk in having EEG data recorded; EEG is a safe and painless noninvasive technique that is routinely used in clinical medicine.

Benefits

Participants may benefit by feeling a reduction in their cravings for opiates. However, we cannot guarantee that they will benefit. The main benefits of this study are to help researchers and clinicians develop a better understanding of craving and substance use after starting opioid treatment.

7.b. Collection and reporting of AEs and SAEs

See 6.a

7.c Management of SAEs and other study risks

See 6.a and 7.a.

8. Trial Efficacy

8.a Plans for interim Analysis of efficacy data

Go/no go criteria for the UG3 phase will be demonstration of greater FMRI change in any node of the CR or CCN networks or enhanced frontal theta power during a WM task AND greater change in subjective craving measured during a cue reactivity task or outside the FMRI following the tDCS+CCN priming intervention compared to sham tDCS+CCN priming.

9. DSM Plan Administration

9.a Responsibility for data and safety monitoring

The Data Safety Monitoring Board will be comprised of 2 individuals independent from this research project. No member of the board will be a collaborator with the MPI on any other studies or have co-published with the MPIs in the past 3 years. They will be qualified to review the patient safety data generated by this study.

They will review rates of adverse events to determine any changes in participant risk and will make appropriate recommendations for changes in protocol, which will be submitted to the Butler Hospital IRB and NIDA for review.

9.b Frequency of DSM

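### The UG3 go/no-go craving condition differs between sections 2.a, 8.a and 2.d, and section 4.c has no UG3 arm comparison of craving to decide it

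*Combined protocol and SAP*

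**What the plan says.** All references are to the combined protocol and SAP.

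- **Section 2.a/2.b** opens the rule with "Go/no go criteria for the UG3 phase will be demonstration of greater fMRI change in any node of the CR or CCN networks", offers enhanced frontal theta power as an alternative, and then adds the craving condition: "AND greater change (at least 10% difference between conditions, controlling for baseline craving) in subjective craving measured during a cue reactivity task". The sentence goes on to allow craving measured outside the scanner instead.
- **Section 8.a**, the section on interim analysis of efficacy data, gives the same rule in almost the same words. Its craving condition reads "AND greater change in subjective craving measured during a cue reactivity task or outside the FMRI following the tDCS+CCN priming intervention". The 10% margin and the adjustment for baseline are absent, and there is no pointer to 2.a.
- **Section 2.d** gives 82% power for an effect size of 0.75 with 24 per group. It says this effect size was chosen partly because the investigators hold that only a large effect should lead on to the UH3.
- **Section 4.c** sets out the UG3 imaging tests ("Significant pre-post main effects and group x treatment interactions are predicted in each"), the node-level follow-up ("Follow up analyses of individual nodes within each network and whole-brain voxel-wise contrasts will be conducted to inform phase 2 analyses") and the theta analysis ("We will conduct a repeated-measures ANCOVA with a within-subject factor of time"). Craving scores enter the UG3 analyses once: "Pearson correlations will be used to examine beta PSD values in relation to craving scores". The arm comparison of subjective craving is written for the UH3, where the hypothesis is that "tDCS+CCN priming will be superior to sham tDCS+CCN priming on both subjective and fMRI measures of craving and cognitive control".

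**The concern.** The rule decides whether a further 100 patients are randomised. Sections 2.a and 8.a both present themselves as the rule and neither is marked as superseded. An adjusted craving difference above zero but below 10% fails 2.a, yet passes 8.a if 'greater' means only in the right direction. An unadjusted difference may satisfy 8.a while the adjusted one that 2.a calls for does not.

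Even if 2.a is taken as the governing text, two analysts could apply it differently in good faith, because the base of the percentage, the measure, the logical grouping and the analysis are all left open. Those choices could then be made after the UG3 data are seen.

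**Working it through.** **1. The plan's own UG3 figure.** Analysed sample: 60 x (1 - 0.20) = 48, or 24 per group. A two-sample t-test with d = 0.75 and 24 per group gives 82.0% power at one-sided alpha 0.05 and 72.0% at two-sided 0.05. The stated 82% therefore reproduces with an unstated one-sided alpha. Two-sided 0.05 with all 30 per arm gives 81.5%, but the text ties the figure to 24. Section 2.d names neither the outcome nor alpha, so it does not settle how a greater change in craving would be judged.

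**2. The texts side by side.**

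| Element | 2.a | 8.a | 2.d |
|---|---|---|---|
| Margin | at least 10% | none | a large effect (0.75 used for sizing) |
| Baseline adjustment | yes | not mentioned | not mentioned |
| Base of the percentage | not given | no percentage | not applicable |
| Craving measure | either of two, neither named | either of two, neither named | not stated |

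**3. Grouping.** Both versions have the form 'A or B AND C', with A = node change, B = theta and C = craving. Read as (A or B) AND C, craving is always required. Read as A or (B AND C), a node change alone suffices. The capitals point to the first reading, but the text does not fix it.

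**4. The missing analysis.** The UG3 analyses in 4.c cover fMRI response, resting coherence, and EEG theta and beta. None has subjective craving as the outcome compared between arms. The UH3 2x3 ANOVA does, but it has neither a 10% margin nor a baseline covariate.

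**5. Illustration of how far the two versions differ (craving condition only).** The documents give no SD, base or correlation. Assumptions: 24 per arm; normal outcome; 10% read as percent of baseline; baseline-adjusted SD of 20, 30 or 50% of baseline; two measures correlated 0.5; 8.a applied to the same adjusted estimate.

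SE = SD x sqrt(2/24) = 5.77, 8.66, 14.43 percentage points.

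No true effect, one measure: P(difference >= 10) = 1 - Phi(10/SE).

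| | SD 20% | SD 30% | SD 50% |
|---|---|---|---|
| 2.a, one measure | 0.042 | 0.124 | 0.244 |
| 2.a, either of two | 0.074 | 0.204 | 0.372 |
| 8.a as direction, one measure | 0.500 | 0.500 | 0.500 |
| 8.a as direction, either of two | 0.667 | 0.667 | 0.667 |
| Passes 8.a, fails 2.a, one measure | 0.458 | 0.376 | 0.256 |

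The last row is the third minus the first.

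If the true effect is 0.75 SD, one measure reaches 10% with probability 0.807, 0.926, 0.972, against 0.995 for direction. The sections then disagree in 0.188, 0.069, 0.023 of trials.

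**6. The disagreement can run the other way.** If 8.a means p < 0.05 on craving (t with 45 df), it needs a difference of 9.7, 14.5, 24.2% one-sided or 11.6, 17.4, 29.1% two-sided. All but the first exceed 10%, so 2.a is then usually the looser rule.

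**7. Where 2.d would sit.** If its standard meant an observed 0.75 adjusted SD, the margin would be 0.75 x 20, 30, 50 = 15, 22.5, 37.5% of baseline, stricter than 10% in each case.

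**The case against.** The strongest reply is that the texts are nested, not opposed. 8.a copies 2.a apart from one parenthesis, and any result that meets 2.a shows a greater change in the right direction, so 2.a reads naturally as the full rule and 8.a as shorthand. That may be what was meant. But 8.a is where a reader would look for the decision rule, it has no cross-reference although 7.b and 7.c just above it do, and nesting fails if 8.a is read as a significance test (step 6). Treating 2.a as the full rule would also leave its open terms open.

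A second reply is that a UG3 craving ANOVA can be inferred, because 4.c says the UH3 imaging analyses broadly follow the UG3 ones and then lists subjective craving. This is a fair inference, but such an analysis would still lack the 10% margin and the baseline covariate.

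Three stronger readings are tempting, and the documents do not support them.

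- A reader might infer that the whole rule is detached from 4.c. The imaging and EEG half has recognisable counterparts there: the network ANOVAs, the node follow-up done to inform phase 2, and the theta ANCOVA. The gap is in craving.
- A reader might infer that letting any single node count is an error that calls for multiplicity control. A lenient screen before a separate randomised trial is a legitimate sponsor's choice, and tightening it would cost sensitivity if only one node responds.
- A reader might infer that UH3 inference is compromised. The UH3 randomises its own 100 participants, so its type I error is untouched.

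**Conclusion.** The concern holds for the craving condition. That 2.a and 8.a differ, and that 4.c has no UG3 arm comparison of craving, follows from the text and needs no assumptions. So do the undefined base, the two unnamed measures, the missing brackets and the unreconciled statement in 2.d.

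The size is illustrative only. With no true effect and one measure, the craving condition is met in about 4-24% of trials under 2.a and 50% under 8.a read as direction. The gap of roughly 26-46 points depends on the assumed SDs and on reading 10% as percent of baseline. These rates cover the craving condition alone and are not false-go rates for the whole decision, which would also depend on the imaging and EEG half and its unknown correlation with craving.

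The header carries a UH3 grant number while section 3.b still treats the UH3 as conditional. A reader might infer that the gate was passed on the weaker wording; the documents do not show which version was used.

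**What to change.** - Put the 2.a rule (10%, adjusted for baseline craving) word for word in 8.a.
- Bracket it so that it is plain whether the craving condition is always required.
- State what the 10% is a percentage of.
- Name the one craving measure that decides.
- Add to 4.c the matching baseline-adjusted UG3 comparison of craving between arms.
- Say whether the large-effect statement in 2.d is part of the rule or only the reason for the sample size.

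How single nodes count, and whether to control multiplicity in this gate, stay with the sponsor.

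**Cost.** No extra patients or data are needed. It is a protocol amendment, and section 6.e requires NIDA approval before it takes effect.

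Naming one measure gives up the chance to pass on the other. Under the assumptions above, if both respond at 0.75 SD, the chance of meeting the craving condition falls from 92% to 81% (SD 20%) or from 99% to 97% (SD 50%). If only the unnamed measure responds, it falls from at least 81, 93, 97% to 4, 12, 24% (SD 20, 30, 50%). The measure should therefore be chosen with care, before unblinding. In return, the chance that an inactive treatment meets the condition falls from 7, 20, 37% to 4, 12, 24%.

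If the go decision has already been taken, rewriting the rule serves little purpose. Record which version, craving measure and analysis were applied.

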The optimal frequency, duration and number of tDCS sessions to maximize effects on craving, or any other construct in this young field, remain obscure. We chose to deliver 5 sessions of tDCS because this number has been used in prior successful tDCS craving interventions and must be balanced against adherence concerns. While we are hopeful that participants will complete 5 consecutive days of tDCS, the interruption of weekends and the transition from the ADP setting (where the tDCS protocol will start) where days are structured, to the community setting, raises the possibility of missed tDCS sessions and therefore we will allow these 5 sessions to occur over 10 days if necessary, as has been described in prior studies, tracking both average number of sessions received and period of treatment for analyses. The sham tDCS condition is included in our design to separate the effects of ongoing opioid treatment from the effect of active tDCS on craving. We decided not to include a third no-tDCS arm, as this would omit any nonspecific treatment effects (match for attention, expectation) of entering a neurostimulation treatment protocol. This protocol will provide a basis for future studies of tDCS stimulation parameters (frequency, duration, number) that could optimize adherence and treatment effects of drug use outcomes.

In phase two (UH3), we will perform a larger RCT using the same treatment protocol in 100 opioid dependent participants who recently initiated buprenorphine or methadone. Participants will be randomized to receive five sessions of tDCS+CCN priming stimulation vs. sham tDCS+CCN priming. Phase two will address long-term (3-month) neurobehavioral outcomes, including opioid relapse, craving, and sustained fMRI changes during a paradigm that challenges networks associated with craving (CR) and cognitive control (CCN). During the 12 weeks of opioid maintenance treatment, we will examine our primary clinical outcome, relapse (opioid use on >4 days per month and having an opioid positive urine screen), as well as days of opioid use.

2.c Inclusion/Exclusion Criteria:

UG3/UH3 Inclusion Criteria: (a) current opioid dependence, (b) between 21-50 years of age, (c) recent initiation of buprenorphine or methadone (<30 days)

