Effect size estimates for baseline differences in fMRI signal based upon subsequent lapse are not available; however we have taken steps to maximize our ability to detect group differences, if present. First, we will use ROI methods, which focus our analyses on more functionally homogenous brain regions related to each task. Therefore, we predict larger and less variable effect sizes. Second, we have chosen fMRI paradigms with which we have already obtained reliable and valid response patterns. Third, the constructs that we propose to assess in fMRI paradigms are significantly related to relapse in behavioral studies.

3. Trial Management:

[figure not shown]
3.a List of Participating enrolling clinics or data collection centers

1. Butler Hospital Alcohol and Drug Partial Hospital Program (ADP)
2. Butler Hospital Alcohol and Drug Inpatient Detoxification Program (ADI)
3. Community Advertisements

3.b Projected Timetable

After staff hiring and training, FMRI programming, and establishing EEG procedures, participant recruitment will begin in month 8 of the UG3 (see below for projected recruitment Timeline). If we proceed to a UH3, we will recruit 100 participants from months 1-29 with the final assessment at month 32. This will leave months 33-36 for data analyses and final manuscript preparation.

UG3 Projected Recruitment Timeline (1UG3DA047793)

3.c Target Population Distribution

In order to increase the percentage of minority subjects in the study, we will over-sample for these groups in our recruitment procedures to obtain a sample that is at least 10% African American and 20% Latino.

Women will be included in this study. We anticipate that the sample will be approximately 40% female based on our experience with previous intervention studies with buprenorphine patients.

4. Data Management and Analysis

4.a, 4.b Data Acquisition and Transition and Data Entry Methods

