A priori task-based FMRI ROI analyses will be our primary method for quantifying changes in the craving, salience and cognitive control networks and subsequent hypothesis testing, while analyses involving the functionally defined ROIs will serve to validate our a priori findings. Mean task-related effect will be determined for each ROI of each individual for each condition of each task by averaging all voxels of each ROI. Results of these quantifications will be used as dependent measures in hypothesis testing. In primary analyses, mean effects will be examined across all nodes of each network, followed by analyses of each network node. Functional connectivity analyses will be performed on all networks during crosshair fixation (resting). We will use the seed region method. Briefly, BOLD signal will be averaged from four 3mm³ seed voxels at the center of mass of each ROI of each network (see Table 1) and extracted for each of the time points acquired. These reference series files will be used as predictors in one voxel-wise GLM analyses per ROI to identify the strength of the relationship between each brain voxel and the average of the seed region over time. Each a priori region will serve as a seed region once for its particular network. After Fischer's transformation from r-values to z-values, the resulting mean voxel-wise values will be averaged in each target node (i.e., ROI not serving as the seed) following each GLM. For CR, these target ROI averages will then be averaged across two seed region iterations (i.e., excluding the seed region; this step is not needed for the 2 ROI salience networks). The resulting means for the nodes of each network will be averaged across ROIs (3 for craving, 2 for salience, 3 for CCN) to derive a network coherence metric. Substance use type (heroin, prescription pills) will be included as a covariate in statistical models.

EEG analyses.

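### No randomisation method is specified, and neither opioid medication nor recruitment source is a named stratum or covariate, so chance imbalance in small arms would go unadjusted

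*Combined protocol and SAP*

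**What the plan says.** **Population.** Section 2.a, 2.b plans the UH3 in "100 opioid dependent participants who recently initiated buprenorphine or methadone"; the UG3 (n = 60) admits the same two medications. Neither phase gives an expected split. Section 3.a lists three sources: the partial hospital programme (ADP), the inpatient detoxification programme (ADI) and "Community Advertisements".

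**Allocation.** The UH3 text reads: "Participants will be randomized to receive five sessions of tDCS+CCN priming stimulation vs. sham tDCS+CCN priming". The UG3 text is equally brief. No sequence generation, blocking, stratification or minimisation is described for either phase. Section 2.a, 2.b does say that the stimulator takes subject-specific codes to deliver active or sham stimulation.

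**Analysis (section 4.c).** Relapse at 3 months is compared with a Pearson chi-square test without adjustment. Craving, imaging and days of use in the UH3 are analysed with a 2x3 ANOVA. The fMRI section names one covariate: "Substance use type (heroin, prescription pills) will be included as a covariate in statistical models". The EEG section adds baseline variables that differ between arms, or predict attrition, at p < 0.05; this rule is stated for the EEG analyses only.

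**Go rule.** Section 2.a, 2.b requires an imaging or frontal theta difference together with a between-arm craving difference of 10% or more, controlling for baseline craving.

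**Setting.** The same section refers to "the transition from the ADP setting (where the tDCS protocol will start) where days are structured, to the community setting".

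**The concern.** The protocol's reason for a sham arm is to isolate stimulation from the opioid treatment that participants are receiving anyway. Randomisation does this on average, but with 30 or 50 per arm a single allocation can leave one arm with visibly more methadone patients or more hospital-recruited patients. Both factors are known at entry, yet nothing in the text balances them at allocation or adjusts for them in the analysis.

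The UG3 is the more exposed phase. It has the smaller arms, and its go decision rests partly on an observed craving difference passing a fixed threshold. A reader of that result could not easily tell a modest stimulation effect from a modest difference in background treatment.

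The text that places the start of stimulation in the ADP also sits awkwardly with three recruitment sources. It is therefore unclear how setting is meant to vary between participants.

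**Working it through.** **1. The plan's own figure (section 2.d).** The UH3 is planned on relapse of 15% vs 39% with 80 evaluable patients and power 0.8. With 40 per arm and alpha 0.05, the normal approximation gives 0.789 one-sided. Two-sided it gives 0.683 (0.692 by exact enumeration of the Pearson chi-square). The stated power therefore reproduces only one-sided. Section 2.d does not state sidedness; that is a separate matter. The 24-point planned difference is the yardstick below.

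**2. Inputs.** Enrolled 60 and 100; evaluable 48 and 80 (section 2.d). Equal arms of 30, 50, 24 and 40 are stated for the UG3 evaluable sample (24 per group) and assumed elsewhere. The share of participants holding a factor, such as methadone, is not given; 30% to 50% is assumed.

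**3. Chance of a 20-point imbalance without stratification.** Two models bracket the unspecified method.
- Independent binomials: X1, X2 ~ Bin(n, p), and the chance is P(|X1 − X2|/n ≥ 0.20).
- Fixed equal arms: of K = 2np factor holders, X ~ hypergeometric(2n, K, n) fall in one arm, and the chance is P(|2X − K|/n ≥ 0.20).

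| Per arm | Binomial, p = 0.3 / 0.5 | Hypergeometric, p = 0.3 / 0.5 |
|---|---|---|
| 30 (UG3 enrolled) | 0.120 / 0.155 | 0.158 / 0.196 |
| 50 (UH3 enrolled) | 0.038 / 0.057 | 0.049 / 0.071 |

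This gives 12% to 20% in the UG3 and 4% to 7% in the UH3. Among evaluable patients the hypergeometric figures are 11% to 15% (24 per arm) and 9% to 12% (40 per arm).

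**4. What an imbalance does to the relapse difference.** Shift = imbalance × relapse gap between factor levels. The gap is not in the documents; 10 to 30 points is assumed.
- Imbalance of 10 to 20 points: 0.10 × 0.10 = 1 point, up to 0.20 × 0.30 = 6 points, which is 4% to 25% of 24 points.
- Typical (1 SD) imbalance with 50 per arm: √(2 × 0.3 × 0.7/50) = 0.092 to √(2 × 0.5 × 0.5/50) = 0.100. With a gap of 20 to 30 points the shift is about 2 to 3 points.
- For scale, the sampling standard error of the difference is √(0.15 × 0.85/50 + 0.39 × 0.61/50) = 8.5 points with 50 per arm, and 9.6 points with 40.

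**5. Would the EEG covariate rule catch it?** At 12/30 vs 18/30 (20 points) the chi-square p-value is 0.12; at 9/24 vs 15/24 (25 points) it is 0.08. Neither meets p < 0.05, so such imbalances would not enter through the between-arm test.

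**6. Gain from stratifying and adjusting.**
- Relapse: simulated with 30% on methadone, 80 evaluable, 15% vs 39%, two-sided 0.05. Medication-stratified randomisation with a CMH test has power of about 0.70, 0.70 and 0.71 for relapse gaps of 10, 20 and 30 points. The unstratified chi-square has about 0.69 throughout. The gain is about 1 to 2.5 points. Type I error is 0.048 to 0.053 either way.
- Continuous outcome: simulated with two binary factors at 30% prevalence. The gain is about 0 to 9 points of power if each factor shifts the outcome by 0.3 to 0.8 SD (assumption). If neither is prognostic, about 1 to 2 points are lost.

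**The case against.** **Silence on method.** A reader might infer that the trial is unstratified or uses simple allocation. The documents do not say so; they are silent on the whole method. The probabilities above are conditional on no stratification. What stands is that the method is unspecified and that neither factor appears in any analysis model.

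**No bias.** A reader might also infer that imbalance would invalidate the comparison. It would not: type I error stays near 0.05, and the standard error already includes this variation. A 6-point shift is a tail case, and the typical shift is well inside sampling error. The relapse power gain is small. This limits the point to precision and interpretability.

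**Prognostic strength not shown.** That medication or setting drives relapse has no source in the documents. The sham rationale implies only that ongoing treatment affects craving, with no size. The relapse gaps above are assumptions.

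**Existing safeguards.** The go rule adjusts for baseline craving and also needs an imaging or theta difference, which removes part of the exposure. The EEG rule bears on the theta route but, as step 5 shows, is likely to miss imbalances of this size. It does not reach craving, relapse or days of use.

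**Recruitment source is a proxy.** Community advertising is a recruitment route, not a treatment setting, and participants may change setting during the sessions. Recruitment source is nevertheless fixed and known at entry, so it can serve as a stratum even if an imperfect one.

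**Design choice.** Stratification, minimisation and covariate adjustment are all defensible at this size. The plan names none of them for these factors.

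**Conclusion.** The point holds as a cheap improvement, not as a flaw that undermines the trial. The plan leaves the randomisation method unspecified and names neither medication nor recruitment source in any analysis. If 30% to 50% of participants hold a factor and no stratification is used, a between-arm difference of 20 points or more has a chance of about 12% to 20% in the UG3 and 4% to 7% in the UH3. The cost is precision and ease of interpretation, greatest for the UG3 go decision. The factor shares, equal arms at enrolment and all prognostic effects are assumptions. No effect on the craving criterion itself can be computed, because the documents give no link between these factors and craving.

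**What to change.** 1. State the randomisation method. Use permuted blocks within medication (buprenorphine, methadone) and recruitment source (hospital programme ADP/ADI, community), with a separate list of the existing stimulator codes for each of the four strata. These average 25 patients at N = 100 and 15 at N = 60.
2. Prespecify the strata as covariates in the UG3 and UH3 craving and imaging models, including those behind the go rule, and in the days-of-use model.
3. Replace the unadjusted relapse chi-square with a CMH or stratum-adjusted analysis, so that the analysis matches the randomisation.
4. Separately, reconcile the statement in section 2.a, 2.b that stimulation starts in the ADP with the three recruitment sources in section 3.a.

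Cost: four lists to manage, protocol and SAP wording, 2 to 3 degrees of freedom, and about 1 to 2 points of power if the factors turn out not to be prognostic. No added patients or visits.
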